#### **4.2 Patient Enrollment and Randomization**

Enrollment will occur when a patient signs and dates an informed consent form and provides authorization to use protected health information.

A total of 60 patients will be randomized into 2 treatment groups in a 1:1 ratio (ticagrelor to clopidogrel). Permuted block randomization will be used to allocate patients to treatment groups. Fixed block sizes will be used to allocate treatment groups, thereby ensuring that sample size in each group is similar as the study progresses. Blocked randomization lists will be computer generated and blinded to the investigators. The investigator will not know the assigned treatment for a patient until the patient is randomization. Patients will not be blinded to their treatment group.

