## **2 Study Design**

## **2.1 Summary**

This is a prospective, randomized, unblinded, open-label, active controlled pilot study to evaluate the efficacy and safety of ticagrelor plus aspirin versus clopidogrel plus aspirin in patients with Rutherford Stage IV to VI PAD that have undergone a percutaneous transluminal angioplasty (PTA) of the lower extremities in the past 2 weeks.

This study will be conducted at the Cleveland Clinic and University Hospital in Cleveland, Ohio. A total of 60 patients are planned for this study.

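### Fixed block sizes in an open-label trial let a recruiter who knows the block size and sees earlier allocations know some upcoming assignments for certain

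*Combined protocol and SAP*

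**What the plan says.** Section 4.2 (Patient Enrollment and Randomization) randomizes 60 patients 1:1: "Permuted block randomization will be used to allocate patients to treatment groups". It then adds: "Fixed block sizes will be used to allocate treatment groups, thereby ensuring that sample size in each group is similar as the study progresses". It gives no block size and does not say whether the size is withheld from recruiting staff.

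On concealment, the same section says: "Blocked randomization lists will be computer generated and blinded to the investigators". It also intends that investigators learn an assignment only once the patient has been randomized. It then states: "Patients will not be blinded to their treatment group".

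Section 2.1 (Summary) is explicit about masking: "This is a prospective, randomized, unblinded, open-label, active controlled pilot study". It names two centres: "This study will be conducted at the Cleveland Clinic and University Hospital in Cleveland, Ohio". Section 4.2 refers to lists in the plural, but does not say whether the centres share one list or each has its own. No stratification by centre is mentioned.

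**The concern.** Concealing the list protects the next assignment only if it cannot be worked out from the past ones. In an open-label trial past assignments are visible. With a known fixed block size, once one arm has used its quota within a block, every remaining assignment in that block is determined, and nobody needs to see the list to know it.

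A recruiter who knows the next assignment can decide whether to approach or enrol a particular patient. The plan leaves room for that. Ability to return for follow-up (section 4.1.1) is a judgement, and randomization may take place before discharge or at the first outpatient visit (sections 4.1 and 7).

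The MMRM in section 9.1 adjusts for post-revascularization TcPO2, which covers part of any such selection. It does not cover selection on features that baseline TcPO2 does not capture, such as wound state or expected adherence. The categorical secondary and safety endpoints, including major adverse limb events, are compared with Fisher's exact test, which has no covariate adjustment. The documents give no figure for how far such selection would move the change in TcPO2, so no bias in mmHg is claimed.

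**Working it through.** **Inputs.** From section 4.2: permuted blocks, fixed size, 1:1, N = 60. From section 2.1: open-label, two centres. The documents state no figure for block size or predictability, so there is none to reproduce. Assumed: block sizes of 4, 6 or 8, and the list structures below.

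**Fixed blocks, all earlier allocations seen.** Write the block size as 2m. An assignment is certain once m patients in the block have gone to one arm. The expected number of certain assignments in a complete block is 2m/(m+1), a share of 1/(m+1).

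- Size 4: 4/3 per block × 15 blocks = 20.
- Size 6: 6/4 = 1.5 per block × 10 blocks = 15.
- Size 8: 8/5 = 1.6 per block × 7 complete blocks = 11.2. The last 4 patients start an eighth block and cannot be certain.

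Simulation gives 20.0, 15.0 and 11.1.

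**Separate list per centre, 30 patients each.**

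- Size 4: 2 × 7 × 4/3 = 18.7.
- Size 6: 2 × 5 × 1.5 = 15.0.
- Size 8: 2 × (3 × 1.6 + 12/70) = 9.9. The term 12/70 is the chance of certainty at positions 5 and 6 of the unfinished block, 2/70 + 10/70.

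**One list shared by both centres, each seeing only its own patients.** Suppose each patient belongs to the first centre with probability q, and the recruiter knows the list position and the block size. Certainty then also requires that all m patients who used up the arm belong to the next patient's centre. This multiplies the full-view count by q^(m+1) + (1−q)^(m+1).

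| Block size | q = 0.5 | q = 0.8 |
|---|---|---|
| 4 | 20 × 0.25 = 5.0 | 20 × 0.52 = 10.4 |
| 6 | 15 × 0.125 = 1.9 | 15 × 0.4112 = 6.2 |
| 8 | 11.2 × 0.0625 = 0.7 | 11.2 × 0.328 = 3.7 |

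**Randomly varied sizes.** These come from simulating lists of 60. The observer sees every allocation and knows the set of sizes but not their order, and the probabilities of the remaining block contents are updated exactly after each patient. Certain assignments: about 3.3 for {4, 6} and 1.4 for {4, 6, 8}. These are upper bounds for a shared list, where less is seen.

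**Best guess, always choosing the more probable arm, full view.**

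| Scheme | Certain, of 60 | Correct guesses |
|---|---|---|
| Fixed 4 | 20 | 71% |
| Fixed 6 | 15 | 68% |
| Fixed 8 | about 11 | 66% |
| Varied {4, 6} | 3.3 | 69% |
| Varied {4, 6, 8} | 1.4 | 68% |

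Pure chance is 50%. On a shared list with fixed blocks of 4, 6 and 8, correct guesses fall to about 60%, 58% and 57% at q = 0.5, and to roughly 60% to 64% at q = 0.8.

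**Effect of the change on balance and power.** With {4, 6, 8} on one list of 60, the final arm difference is 0 in 72% of lists, 2 in 27% and 4 in 0.4%; it cannot exceed 4, half the largest block. With separate lists of 30, the differences 0, 2, 4 and 6 occur in about 56%, 39%, 4.3% and under 0.1% of runs, and the maximum is 8.

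For power I used a two-sample t test, two-sided 0.05, a difference of 8 mmHg, and an SD of 9.40 mmHg chosen so that 30 v 30 gives the 90% stated in section 9.2. Power depends on the split through 1/n1 + 1/n2:

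- 30 v 30: 0.06667, power 90.0%.
- 31 v 29: 0.06674, power 89.97%.
- 32 v 28: 0.06696, power 89.87%.
- 34 v 26, the extreme with separate lists: 0.06787, power 89.5%.

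**The case against.** **Guessing.** A recruiter can act on the likelier arm and need not wait for certainty, and varied blocks barely alter that. If the undisclosed size is 6, {4, 6, 8} gives no gain in guessing; if it is 8, guessing becomes slightly easier (66% to 68%). This stands. The change removes most certain foreknowledge, not selection bias as a whole.

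**The conditions may not be met.** Nothing in the documents shows that recruiters know the block size, and leaving it out of the protocol helps concealment. The plural in the text does not settle whether a single size is used throughout. With no stratification by centre, one shared list is a natural reading, and the counts are then much smaller. All this is fair, and it is why the result is conditional and given as a range. It does not protect against someone inferring a fixed size from open allocations.

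**Little room to exploit it.** The synopsis plans 60 patients over 48 months, 1.25 a month or one about every 24 days, while the intervention must fall within the past 2 weeks. Holding a patient for a preferred slot would often breach that window. This narrows the risk, but choosing not to approach a patient remains possible, and slow accrual makes past allocations easy to track.

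**Partly covered already.** Baseline TcPO2 is adjusted for, and wound size and Rutherford class are recorded, so selection on wound state might be noticed. Comparing baselines would not correct it.

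**Conclusion.** The concern holds as a conditional design weakness that should be fixed. If the block size is known or inferred and all earlier allocations on the list are visible, fixed blocks of 4 to 8 make about 11 to 20 of 60 assignments certain in advance, or 10 to 19 with separate centre lists. Varied, undisclosed sizes bring the full-view count down to about 1 to 3. On one shared list with partial views the present exposure is 0.7 to 5.0 at an even split and 3.7 to 10.4 at 80:20, so the gain is small with larger blocks and an even split.

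The counts rest on assumed block sizes and list structures, because the plan states neither. No contradiction, actual bias or bias in mmHg is shown. The stated reason for fixed blocks, similar group sizes as the study progresses, is kept almost entirely with varied sizes.

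**What to change.** In section 4.2, replace fixed block sizes with randomly varied ones, for example 4, 6 and 8. State that the sizes and their order are withheld from the sites.

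Two clarifications belong in the same edit. State whether the two centres share one list. State that the assignment is released only after eligibility and baseline TcPO2 have been recorded. The second only makes an existing order explicit, since a baseline TcPO2 below 10 mmHg is already an exclusion (section 4.1.2) and section 6.1 lists the measurement before randomization.

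The cost is an edit of a few sentences and a regenerated list for patients not yet randomized; N stays at 60. If recruitment has begun, complete the open block before switching, so that it adds no imbalance of its own. The likely final difference between arms is 0 or 2 patients, and the loss of power is about 0.1 percentage points at most on one list, or 0.5 at the extreme with separate lists.

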#### **4.3 Study Withdrawal**

Patients are free to withdraw their participation at any time during this clinical study. The investigator also has the right to discontinue treatment with study drug if a serious adverse reaction to the study drug occurs. Patients will be encouraged to remain in the study even if study drug is discontinued. Reasons for early withdrawal of any patient from the study will be documented in the medical records. If the reason for discontinuation of the study drug is from an adverse event it will be documented in the medical records and the case report forms.

#### **4.4 Study Discontinuation**

The sponsor has the right to terminate the study at any time based on a recommendation from the Medical Monitor.

### **5 Treatment of Patients**

#### **5.1 Treatment Regimen**

Patients are placed on clopidogrel after their arterial intervention per SOC. They will remain on clopidogrel up to the time that randomization occurs. For patients that are randomized to ticagrelor, the clopidogrel will be stopped.

Study Drug	Dose Level and Frequency
clopidogrel	75 mg by mouth daily
ticagrelor	90 mg by mouth twice daily

## **5.2 Description of Study Drug**

Clopidogrel (Plavix®) is an FDA approved P2Y12 platelet inhibitor indicated for use in patients with acute coronary syndrome, recent MI, recent stroke, or established peripheral arterial disease. See Appendix A for a complete description of the drug.

Ticagrelor (Brilinta®) is an FDA approved P2Y12 platelet inhibitor indicated to reduce the rate of thrombotic cardiovascular events in patients with acute coronary syndrome (ACS) (unstable angina, non-ST elevation myocardial infarction, or ST elevation myocardial infarction). See the Investigator Brochure for a complete description of the drug.

## **5.3 Obtaining Study Drugs**

Study medication (ticagrelor) will be provided for the patients from randomization until the time of the 6 month visit.

## **5.4 Concomitant Medications**

Patients should receive aspirin 81 mg by mouth every day as per labeling recommendations for ticagrelor and clopidogrel.

## **5.5 Prohibited Medications**

Treatment with the following medications are excluded during this study:

- Aspirin doses greater than 100 mg per day
- Oral anticoagulation with a vitamin K antagonist
- Factor Xa inhibitors
- Direct thrombin inhibitors

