Prohibited Medications	
 
• Concomitant use of oral anticoagulation with a vitamin K antagonist, factor Xa inhibitor, or direct thrombin inhibitor
 
• Aspirin > 100mg per day
 

Endpoints	
Primary endpoint
 
 
• Absolute change in TcPO2 from baseline to 6 months
 
 
Secondary endpoints
 
 
• Rate of wound healing from baseline to month 6 in treatment groups for patients with Rutherford Stage V-VI PAD
 
• Change in ankle-brachial index (ABI), toe-brachial index (TBI), toe-systolic pressure (TSP) and skin perfusion pressure (SPP) from baseline to month 6 in treatment groups
 
• Major adverse limb events including a composite of surgical limb loss or any major vascular repeat revascularization, including thrombectomy, thrombolysis, or major lower-extremity surgical procedure from baseline to month 6 in treatment groups
 
• Percent change in TcPO2 from baseline to 6 months
 
• Percent change and absolute change in TcPO2 from baseline to month 3
 

AE/ SAE Collection	
AEs
 
 
• Self-reported shortness of breath with symptomatic bradycardia
 
• Events that are not listed in the current labeling for the drugs
 
• Events that lead to discontinuation of drug or result in a dose modification
 
 
SAEs
 
 
• Death.
 
• Life threatening AEs.
 
• Requires inpatient hospitalization or prolongation of existing hospitalization.
 
• A disability/incapacity.
 
• A congenital anomaly/birth defect in the offspring of a patient who received drug.
 
• Important medical event that may jeopardize the subject or may require medical intervention to prevent one of the outcomes listed above.
 
 
Other SAEs of Special Interest
 
 
• Major bleeding defined as a composite of fatal bleeding, intracranial bleeding, hypovolemic shock or severe hypotension due to bleeding requiring pressors, or need for transfusion of at least 2 units in any 24-hour period.
 
• Major adverse limb events (surgical limb loss, major repeat revascularizations including thrombectomy, thrombolysis, or major lower extremity surgical procedure.
 

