Similar to the endovascular treatment of coronary artery disease, percutaneous transluminal angioplasty (PTA) for PAD requires the use of dual-antiplatelet therapy (DAPT) to prevent thrombotic complications related to stent placement or balloon angioplasty. In a head-to-head comparison with clopidogrel among patients with acute coronary syndromes, ticagrelor has already shown impressive reductions in mortality without increasing the overall risk of major

bleeding (13). For patients undergoing PTA, DAPT is recommended for at least 30 days following the PTA procedure. The benefits of DAPT beyond 30-days after peripheral arterial intervention have been recently demonstrated; clopidogrel plus aspirin was superior to aspirin monotherapy for up to 6 months after PTA by preventing peri-procedural platelet activation and improved functional outcomes without increasing the risk of bleeding complications (14). Furthermore, even though costs associated with long-term DAPT are higher, clopidogrel has proven cost-effective over aspirin monotherapy for secondary prevention for vascular events among patients with PAD (15,16). With an anticipated antiplatelet benefit as robust as that of clopidogrel, ticagrelor may also demonstrate cost-effectiveness.

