#### **4.1.2 Exclusion Criteria**

Patients will be ineligible for this study if they meet any one of the following criteria:

1. Intolerance to thienopyridines
2. Hypersensitivity to ticagrelor or any component of the product
3. Concomitant use of oral anticoagulation with vitamin K antagonist, factor Xa inhibitor, or direct thrombin inhibitor
4. History of intracranial hemorrhage
5. History of severe hepatic impairment defined by baseline transaminase greater than or equal to 3x ULN or any elevation in bilirubin
6. Active bleeding
7. Allergy to aspirin
8. Baseline TcPO2 < 10 mmHg post angiography
9. Resting pre-procedure heart rate < 50 beats-per-minute without a permanent pacemaker and not on an atrioventricular nodal blocking agent
10. Severe COPD on home oxygen therapy
11. Patients on strong CYP3A inhibitors and/or CYP3A inducers that cannot be stopped for the course of the study. \*

- \* Strong inhibitors of CYP3A are the following medications: ketoconazole, itraconazole, voriconazole, clarithromycin, nefazodone, ritonavir, saquinavir, nelfinavir, indinavir, atazanavir and telithromycin.  
Potent inducers of CYP3A include the following medications: rifampin, dexamethasone, phenytoin, carbamazepine and phenobarbital.  
In addition, ticagrelor will result in higher serum concentrations of simvastatin and lovastatin because these drugs are metabolized by CYP3A4 and doses greater than 40 mg with these medications should be avoided.

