### Metabolism

Clopidogrel is extensively metabolized by two main metabolic pathways: one mediated by esterases and leading to hydrolysis into an inactive carboxylic acid derivative (85% of circulating metabolites) and one mediated by multiple cytochrome P450 enzymes. Cytochromes first oxidize clopidogrel to a 2-oxo-clopidogrel intermediate metabolite. Subsequent metabolism of the 2-oxo-clopidogrel intermediate metabolite results in formation of the active metabolite, a thiol derivative of clopidogrel. This metabolic pathway is mediated by CYP2C19, CYP3A, CYP2B6 and CYP1A2. The active thiol metabolite binds rapidly and irreversibly to platelet receptors, thus inhibiting platelet aggregation for the lifespan of the platelet.

The Cmax of the active metabolite is twice as high following a single 300 mg clopidogrel loading dose as it is after four days of 75 mg maintenance dose. Cmax occurs approximately 30 to 60 minutes after dosing. In the 75 mg to 300 mg dose range, the pharmacokinetics of the active metabolite deviates from dose proportionality: increasing the dose by a factor of four results in 2- and 2.7-fold increases in Cmax and AUC, respectively.

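### Strong CYP3A inhibitors and CYP3A inducers are an entry exclusion but are missing from both on-study prohibited lists, so starting one after randomization breaks no stated protocol rule

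*Combined protocol and SAP*

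**What the plan says.** Section 4.1.2, criterion 11, repeated under Key Selection Criteria in the synopsis, excludes "Patients on strong CYP3A inhibitors and/or CYP3A inducers that cannot be stopped for the course of the study". Its footnote names the drugs. The inhibitor sentence begins "Strong inhibitors of CYP3A are the following medications: ketoconazole, itraconazole, voriconazole, clarithromycin" and goes on to seven more; the inducer sentence reads "Potent inducers of CYP3A include the following medications: rifampin, dexamethasone, phenytoin, carbamazepine and phenobarbital". The footnote then warns that ticagrelor raises simvastatin and lovastatin levels and advises against doses of either above 40 mg.

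The on-study rules are in two places. Section 5.5 begins "Treatment with the following medications are excluded during this study" and has four entries: aspirin above 100 mg per day, vitamin K antagonists, factor Xa inhibitors and direct thrombin inhibitors. The Prohibited Medications row of the synopsis gives the same content. Section 5.4 covers only the daily aspirin 81 mg.

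Concomitant medications are recorded at baseline, month 3 and month 6 (sections 6.1 to 6.3). Section 4.3 encourages patients to remain in the study after stopping study drug, and section 9.1 specifies intent-to-treat comparisons.

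**The concern.** An exclusion criterion is applied once, at entry. Criterion 11 reaches a patient who is already taking one of these drugs at screening. It does not reach a patient who is first prescribed one in, say, month 2. For that patient the operative text is section 5.5, and a coordinator who checks it finds nothing to flag.

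Criterion 11 asks that these drugs be stopped for the whole study, so the sponsor evidently wants patients kept off them throughout. As written, the on-study rule permits, for up to six months of treatment, co-medication that the entry rule treats as unacceptable. The footnote includes antibiotics and antifungals, and the population includes patients with ischemic ulcers or gangrene (Appendix B, stages 5 and 6). New anti-infective prescriptions are therefore plausible, although that is an inference and the documents give no rate. What is at stake is patient safety and agreement between two parts of the protocol.

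**Working it through.** The plan gives no figure on this point, so the check is a comparison of text.

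**Step 1. Carry-over from entry criteria to on-study lists.** Exclusion 3 reads "Concomitant use of oral anticoagulation with vitamin K antagonist, factor Xa inhibitor, or direct thrombin inhibitor". The synopsis prohibited list reads "Concomitant use of oral anticoagulation with a vitamin K antagonist, factor Xa inhibitor, or direct thrombin inhibitor", and section 5.5 lists the same classes separately.

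| Drug class | Entry criterion | Section 5.5 | Synopsis prohibited list |
|---|---|---|---|
| Vitamin K antagonist | 3 | yes | yes |
| Factor Xa inhibitor | 3 | yes | yes |
| Direct thrombin inhibitor | 3 | yes | yes |
| Strong CYP3A inhibitor | 11 | no | no |
| CYP3A inducer | 11 | no | no |

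Anticoagulant classes carried over: 3 of 3 on both lists. CYP3A classes carried over: 0 of 2 on either list.

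**Step 2. Drugs named.** The footnote names 11 inhibitors (ketoconazole, itraconazole, voriconazole, clarithromycin, nefazodone, ritonavir, saquinavir, nelfinavir, indinavir, atazanavir, telithromycin) and 5 inducers (rifampin, dexamethasone, phenytoin, carbamazepine, phenobarbital): 11 + 5 = 16.

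**Step 3. Is there a rule for new starts elsewhere?** CYP3A is mentioned in three places:
- The synopsis selection criteria: an entry test.
- Section 4.1.2, criterion 11 and footnote: an entry test, a drug list and the statin advice. The statin advice does apply on treatment, but it concerns drugs metabolized by CYP3A4, not inhibitors or inducers.
- Appendix A, clopidogrel label section 12.3, on formation of the active metabolite: "This metabolic pathway is mediated by CYP2C19, CYP3A, CYP2B6 and CYP1A2". This is pharmacology and sets no rule.

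Places that bar a new start of an inhibitor or inducer after randomization: 0 of 3. Sections 4.3, 5.4 and 6.1 to 6.3 add none.

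**Step 4. Which arm?** Criterion 11 applies to every patient at entry. However, the interaction section of the clopidogrel label (Appendix A, section 7) covers CYP2C19 inhibitors, NSAIDs and warfarin and has no warning about CYP3A inhibitors or inducers. The case for an on-study restriction is therefore clearer for ticagrelor. For clopidogrel it rests on matching the entry rule and on the one pharmacology sentence quoted in step 3.

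**The case against.** **Interactions may have been left to the labelling.** Section 5.5 does not call itself exhaustive. It also omits cautions from the appended clopidogrel label, such as avoiding omeprazole and esomeprazole and the bleeding risk with NSAIDs. Sections 5.2 and 8.1 refer to the Investigator Brochure, which was not available. This stands as a limit: it cannot be said that sites have no guidance on ticagrelor interactions. It does not close the gap. Section 5.2 cites the brochure as a drug description and section 8.1 cites it for labelled events; neither makes it an on-study medication rule. The CYP3A classes also differ from the omitted label cautions, because the sponsor wrote them into the protocol as an entry restriction.

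**The ban is implied.** A sensible investigator may read it that way for a patient who was taken off such a drug to enter. Nothing extends it to a first prescription after randomization.

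**Exposure will be seen anyway.** Concomitant medications are recorded at each visit, and under section 10.2 a Medical Monitor reviews case report forms. That stands and lowers the priority. But recording is not prohibition, and with scheduled visits three months apart a short course can be over before the study team learns of it.

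**A reader might infer more than the text supports.**
- *That ticagrelor must be held if one of these drugs becomes necessary.* No passage supports this, and it could do harm. Patients enter within 2 weeks of the intervention, and section 1.2 says "For patients undergoing PTA, DAPT is recommended for at least 30 days following the PTA procedure". A patient randomized on day 14 still has 30 − 14 = 16 days of that period left. Section 7 describes ADP-receptor therapy as routinely continued for 6 months. If clopidogrel is used as cover, the patient crosses to the comparator; section 9.2 allows 5% crossover, which is 0.05 × 30 = 1.5 ticagrelor patients.
- *That the clopidogrel arm needs the same ban.* The clopidogrel label's interaction section does not say so; it would be a choice for symmetry.
- *That the protocol fails to say when a stoppable drug must be stopped.* Randomization and dispensing are baseline procedures (section 6.1), so the natural reading is off the drug from entry. Only a washout interval is unstated, and nothing in the documents shows that one is needed.

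**Conclusion.** The point holds as a minor inconsistency in the protocol. The entry rule wants patients free of two drug classes for the study, and the on-study lists omit both (0 of 2) while repeating every anticoagulant class from the entry rule (3 of 3). Starting one of the 16 named drugs after randomization breaks no stated protocol rule.

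The conclusion rests on the protocol text and the appended clopidogrel label; the Investigator Brochure could not be checked. That these drugs are unwanted with ticagrelor is inferred from criterion 11. The documents give no interaction size, no frequency of use and no effect on bleeding, dyspnea, bradycardia or TcPO2, so the consequence cannot be quantified. A reader might infer a threat to the primary comparison; the documents do not support that, and no effect on power, type I error or the primary analysis is claimed.

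**What to change.** Add one line to section 5.5 and to the Prohibited Medications row of the synopsis: strong CYP3A inhibitors and potent CYP3A inducers, as named in section 4.1.2. Apply it at least to patients taking ticagrelor, and to both arms if the sponsor wants the on-study rule to mirror the entry rule.

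Add a short rule for unavoidable use. The investigator decides on P2Y12 therapy so that antiplatelet cover is maintained; the exposure is recorded on the existing concomitant-medication form; and the patient stays in follow-up and in the intent-to-treat analysis, in keeping with sections 4.3 and 9.1. Do not mandate holding ticagrelor.

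The cost is a few lines of text that reuse drug names already in the protocol. The downside is a few more recorded deviations and a limit on some co-medications. Sample size and analysis are unchanged.
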